3.5. Success Criteria of Study

Three different doctors will evaluate the volunteer's fundus images taken from fundus cameras and will make a decision about the presence of DR: Not more than Mild DR, More than mild DR (mtmDR), and Vision-threatening DR (vtDR). Decisions will be made by majority vote. The doctors' decision will be Ground Truth for us.

EyeCheckup will decide for both eyes of each volunteer. If it is the same as the doctors' decision, this decision will be considered correct.

Total correct number / Total number of eyes = Success rate

Our criteria for successful completion of the clinical trial: Success rate > 90%

EC-2021DR-TR DETECTION AND CLASSIFICATION OF DIABETIC RETINOPATHY FROM POSTERIOR POLE IMAGES WITH A DEEP LEARNING MODEL

At the same time, the Specificity and Sensitivity values should be calculated separately for mtmDR and vtDR and each should be above 90%.

Eye doctors (Normal, mtmDR, vtDR) make their decisions according to the ETDRS guidelines. Main signs to check for: Microaneurysms, Intreretinal hemorrhages (Intraretinal hemorrhage), Venous beading, IRMA, Neovascularization, Intravitreal hemorrhage, Preretinal hemorrhage

3.6. The benefit of the Research, Possible risks and precautions to be taken against harm:

Benefits;

According to the 2018 data from the World Health Organization, 285 million people worldwide have a visual impairment. It is known that more than 80% of all visual disorders can be prevented or treated. The retinal examination should be performed by an ophthalmologist and/or retinal specialist in order to prevent retinal-related visual disorders by making an accurate diagnosis, but people only consult an ophthalmologist when they feel any discomfort. Typically, by the time symptoms appear, the disease has reached advanced stages and requires a variety of expensive medical and surgical treatments. Unfortunately, at this stage, the disease often results in severe and permanent visual impairment and vision loss.

EyeCheckup analyzes the patient's fundus/retinal health with images taken from the fundus camera. If it sees a problem, it directs the patient to the doctor, if not, it recommends scanning again after an appropriate period of time recommended within the AAO PPP. Thanks to the early detection of eye problems, early diagnosis and treatment can prevent vision loss and visual impairment. The most important aim of EyeCheckup is the early diagnosis of diabetic retinopathy and thus the prevention of possible vision loss and blindness. Secondary objectives of EyeCheckup are using less trained manpower and screening for DR in populations without access to an ophthalmologist.

Possible Risks;

The images used in our study do not pose any risk or harm to the patients. Only fundus images of the patients will be evaluated. The images will be recorded anonymously, and doctors or the Artificial Intelligence algorithm will not be able to access the identity and health information of the patients. There will be no harmful use of personal data or health information.

The study is expected to pose minimal risk to both camera operators and participants, as the camera systems used have been previously approved by the FDA for ocular fundus photography, and tropicamide 1% eye drops for pupil dilation is an FDA-approved drug product and have been shown to have minimal side effects.

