3.1. Summary of Clinical Findings

All documents required by the standard for EyeCheckup software have been created, risk analysis has been made and precautions have been taken against possible risks.

EyeCheckup clinical trial will be performed in a single center at Akdeniz University Hospital. The target population is people aged 18 and over, who have been diagnosed with diabetes in the Endocrinology Clinic of Akdeniz University Hospital and have not been diagnosed with diabetic retinopathy (DR) before, and whose retinal image can be taken. To better align the analysis population with the proposed target population, those who do not meet certain additional predetermined criteria (eg: less than 18 years of age, visually impaired) will be excluded. Volunteers will be taken to the research area allocated by the hospital at Akdeniz University. Before any volunteers are recruited, candidates will need to verify that they understand the research and have given written informed consent. Study; **CE marking will** be made to measure the success of Artificial Intelligence software in terms of specificity and sensitivity, which detects the presence of mild DR (mtmDR) and vision-threatening DR (vtDR) for each eye by taking retinal images from 3 different fundus cameras and using these images.

The artificial intelligence model was trained with fundus images taken from Akdeniz University Hospital Ophthalmology Clinic with the approval of the Akdeniz University Ethics Committee.

The publicly available Kaggle Diabetic Retinopathy Detection Competition (EyePACS dataset), Kaggle APTOS 2019 Blindness Detection Competition dataset, Messidor, Messidor 2, IDRiD Dataset, and DIARETDB0 - Standard Diabetic Retinopathy Database datasets were used as test datasets. A retrospective study was performed on a total of 4000 test images (dataset). As a result of the test studies, more than 92% specificity and 92% sensitivity were obtained. The result of the most successful algorithm is listed below. The most successful algorithm was built on the Google ML Platform, and this first prototype will be used as a Non-CE Marked Medical Device Research (Excluding Thesis and Academic Studies).

Diagnosis	Truth
normal eye	97.19%
Mild/Moderate Diabetic Retinopathy	96.43%
Severe / Proliferative Diabetic Retinopathy	100.00%
Diabetic Macular Edema	100.00%

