3.4. Rationale / Importance and Contribution of the Research

EyeCheckup is an automated software instrument designed to analyze digital color photographs of the ocular fundus to quickly screen for diabetic retinopathy (DR).

The main purpose of the study was to detect the presence of mild diabetic retinopathy or sight-threatening diabetic retinopathy from retinal fundus images in adult patients who applied to the endocrinology outpatient clinic due to diabetes, to grade and to determine the sensitivity and specificity of diabetic retinopathy, and to identify and classify the images with the developed

artificial intelligence algorithm. It is a comparison of diagnosis done by artificially intelligent algorithms and classification of DR done by doctors.

The primary efficacy endpoint in the study was that EyeCheckup's intended image capture workflow could be successfully used in conjunction with the EyeCheckup device to diagnose 80% or more of the participants for more than mild diabetic retinopathy (mtmDR) and vision-threatening diabetic retinopathy (vtDR) separately with a minimum 90% sensitivity and 90% specificity.

The secondary efficacy endpoint in the study was

Additional non-primary analyzes will also be performed to assess the following general conditions:

- Positive Predictive Value of EyeCheckup test for mtmDR and vtDR,
- Negative Predictive Value EyeCheckup test for mtmDR and vtDR.
- Positive and negative odds ratios for mtmDR and vtDR.

The study will include approximately 900 people with diabetes, excluding exclusions. They will be recruited voluntarily through 1 clinical center. Two photographs of the ocular fundus (one optic disc centered, one macula centered) will be obtained per eye using a non-mydriatic eye fundus camera from both eyes of the participants. These images will be analyzed by EyeCheckup. Then, pupil dilation will be achieved by instilling Tropicamide drops in both eyes of the patient and 4 quadrant photographs of both eyes will be taken with a fundus camera. Ophthalmologists will then evaluate and record the condition of the eyes based on images obtained with pupil dilation.

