6. STATISTICS

6.1. Analysis

Fundus images of 900 volunteer patients with evaluable quality, with or without pathology, who applied to Akdeniz University Endocrinology and Metabolism Diseases Department with the diagnosis of diabetes, were not diagnosed with Diabetic Retinopathy before, and whose images can be obtained from the posterior polar region of the eye with a fundus camera, will be included in the study, which will be carried out as a single-center study. The sample size was determined by Akdeniz University Statistics Consultancy Application and Research Center, taking into account the incidence of diabetic retinopathy in diabetic patients. Upon confirmation that the Al algorithm is working successfully, the trial will be terminated when the intended number of 900 patients is reached. The success criterion of the study is specified in Article 3.5.

The classification performance of the AI algorithm will be evaluated with reference to the diagnosis made by the doctors. Gold standard test results will be obtained based on the diagnosis from three different doctors. At this stage, the compatibility between the diagnosis from the doctors will be evaluated according to the Kappa statistics, and the similarity of the decisions made by the doctors with each other will be examined. The diagnoses of the patients will then be evaluated together with the results of the AI algorithm, and performance measures of the AI algorithm (sensitivity, selectivity, positive predictive value, negative predictive value, overall accuracy, etc.) will be obtained. Whether the performances of the AI algorithm are clinically acceptable or not will be evaluated with ratio tests (single sample population ratio significance test, Fisher Exact test, Chi-square tests, etc.) according to the threshold values to be determined by experts. A data analysis software will be selected among various software (R, SPSS, TURCOSA, Stata, etc.) to do the statistical analysis in accordance with the purpose. For statistical analysis, the level of significance will be taken as 0.05. (Annex-1 Analysis Plan)

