6.2. Determination of Sample Size

The sample size was calculated by evaluating whether the Al algorithm achieved a success rate of more than 90%, considering 5% Type-I error, 80% power, and different effect sizes listed below.

Prop	ortion	Proportion					
		Given H0	Given H1	Target	Actual		Reject H0
Power	N	(P0)	(P1)	Alpha	Alpha	Beta	If Z>=This
0,8033	5341	0,9000	0,9100	0,0500	0,0511	0,1967	1,6449
0,8002	2286	0,9000	0,9150	0,0500	0,0520	0,1998	1,6449
0,8015	1255	0,9000	0,9200	0,0500	0,0525	0,1985	1,6449
0,8004	778	0,9000	0,9250	0,0500	0,0530	0,1996	1,6449
0,8012	523	0,9000	0,9300	0,0500	0,0541	0,1988	1,6449
0,8047	376	0,9000	0,9350	0,0500	0,0545	0,1953	1,6449
0,8092	284	0,9000	0,9400	0,0500	0,0539	0,1908	1,6449
0,8076	212	0,9000	0,9450	0,0500	0,0565	0,1924	1,6449
0,8004	164	0,9000	0,9500	0,0500	0,0553	0,1996	1,6449

Considering the situation marked in the table above as an example, if at least 778 people are included in the study, the case that the Al algorithm will achieve at least 2.5% above the 90% level can be detected at 80% power and 5% type-1 error level. If the success rate of the Al algorithm increases at a level of 2.5% or less from 90%, this difference will not be statistically significant. (Annex-1 Analysis Plan)

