ANNEX-1 ANALYSIS PLAN

The diagnosis of the patients will be made by 3 doctors by evaluating the images and a joint diagnosis decision will be made by combining the diagnosis made by the doctors for each patient. This diagnosis will be considered the "Gold Standard" for the study. With the developed Al algorithm, it will be investigated to what extent the diagnosis made by the doctors can be predicted. The Al algorithm developed for the diagnosis of DR is expected to achieve a success rate of 90% or more. A success above this level will show that the developed Al algorithm will be usable. For this purpose, whether the Al algorithm achieves a success rate of 90% or more will be investigated with the one-way hypothesis pair given below.

$$H_0: P = 0.90 H_1: P > 0.90$$

The sample size was calculated by evaluating whether the Al algorithm achieved a success rate of more than 90%, considering 5% Type-I error, 80% power, and different effect sizes listed below.

Prop	ortion	Proportion					
_		Given H0	Given H1	Target	Actual		Reject H0
Power	N	(P0)	(P1)	Alpha	Alpha	Beta	If Z>=This
0,8033	5341	0,9000	0,9100	0,0500	0,0511	0,1967	1,6449
0,8002	2286	0,9000	0,9150	0,0500	0,0520	0,1998	1,6449
0,8015	1255	0,9000	0,9200	0,0500	0,0525	0,1985	1,6449
0,8004	778	0,9000	0,9250	0,0500	0,0530	0,1996	1,6449
0,8012	523	0,9000	0,9300	0,0500	0,0541	0,1988	1,6449
0,8047	376	0,9000	0,9350	0,0500	0,0545	0,1953	1,6449
0,8092	284	0,9000	0,9400	0,0500	0,0539	0,1908	1,6449
0,8076	212	0,9000	0,9450	0,0500	0,0565	0,1924	1,6449
0,8004	164	0,9000	0,9500	0,0500	0,0553	0,1996	1,6449

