The diagnostic performance of the AI algorithm will be evaluated with reference to the decisions made by the doctors. Gold standard test results will be obtained based on the diagnosis provided by three different doctors. At this stage, the compatibility between the diagnosis from the doctors will be evaluated according to the Kappa statistics, and the similarity of the diagnosis made by the doctors with each other will be examined. The diagnoses of the patients will then be evaluated together with the results of the AI algorithm, and performance measures of the AI algorithm (sensitivity, selectivity, positive predictive value, negative predictive value, overall accuracy, etc.) will be obtained. Whether the performances of the AI algorithm are clinically acceptable or not will be evaluated with ratio tests (single sample population ratio significance test, Fisher Exact test, Chi-square tests, etc.) according to the threshold values to be determined by experts. A data analysis software will be selected amongst various softwares (R, SPSS, TURCOSA, Stata, etc.) to do the statistical analysis in accordance with the purpose. For statistical analysis, the level of significance will be taken as 0.05.

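### The success rate is counted per eye, but the analysis plan is written for people, names only tests for independent observations and gives no method for paired eyes

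*Combined protocol and SAP*

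**What the plan says.** **Eye as the unit.** Section 3.5 gives the only formula for the success rate: "Total correct number / Total number of eyes = Success rate". It also says that "EyeCheckup will decide for both eyes of each volunteer". Section 6.1 defers to this: "The success criterion of the study is specified in Article 3.5". Section 3.1 describes the software as one "which detects the presence of mild DR (mtmDR) and vision-threatening DR (vtDR) for each eye".

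**Person or patient as the unit.** Section 6.2, repeated in Annex-1, explains the highlighted sample-size row with the words "if at least 778 people are included in the study". Annex-1 sets the reference standard so that "a joint diagnosis decision will be made by combining the diagnosis made by the doctors for each patient". Its Statistical Analysis Plan part continues: "The diagnoses of the patients will then be evaluated together with the results of the AI algorithm".

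**Sensitivity and specificity.** Section 3.5 requires each to exceed 90% for mtmDR and for vtDR, without naming the unit. The primary endpoint in Section 3.4 speaks of the ability "to diagnose 80% or more of the participants".

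**Methods.** Section 6.1 and Annex-1 list a one-sample proportion test, Fisher's exact test and chi-square tests, and leave the list open. No section mentions a within-person correlation, a design effect or a clustered analysis. The only rule for combining results is across the three doctors. None is given for the two eyes of one person.

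**The concern.** Two eyes of one person share the disease, the photographer, the visit and much of the image quality. Whether the software is right in one eye is therefore likely to be related to whether it is right in the other. The tests named in the plan take every observation as independent. Applied to the per-eye rate of Section 3.5, they use a standard error that is too small whenever that correlation is positive. The formal test then rejects too often at a true rate of 90%, and confidence intervals are too short.

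The person-based wording of Section 6.2 and Annex-1 does not solve this, because it does not say whether the tested proportions are per eye or per person. An analyst who follows the text literally has an eye-level rate, a list of tests for independent data and no instruction on pairing. The same gap affects intervals and tests for sensitivity and specificity.

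**Working it through.** **Inputs from the documents.** P0 = 0.90, one-sided alternative, rejection if Z ≥ 1.6449, 80% power, N = 778 for P1 = 0.925 (Section 6.2 and Annex-1); about 900 people planned (Section 3.4); two eyes per volunteer (Section 3.5).

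**Assumption.** rho, the within-person correlation of a correct decision, is not in the documents. The range 0 to 1 is shown. All figures for 900 volunteers take 900 complete pairs.

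**Step 1: reproduce the plan's row.** The cut-off is 778 × 0.90 + 1.6449 × √(778 × 0.09) = 713.96, so 714 correct. Exact binomial probabilities give alpha 0.0530 and power 0.8004, both equal to the table. The table is right for 778 independent units.

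**Step 2: apply the same test to eyes as if independent.** The cut-off is 1,800 × 0.90 + 1.6449 × √(1,800 × 0.09) = 1,640.9, so 1,641 correct eyes. For one volunteer with per-eye rate p:

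- P(both correct) = p² + rho·p(1 − p)
- P(exactly one correct) = 2p(1 − p)(1 − rho)
- P(neither correct) = (1 − p)² + rho·p(1 − p)

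The true variance of the rate is p(1 − p)/1,800 × (1 + rho), so an interval that ignores pairing is too narrow by a factor √(1 + rho). Exact enumeration over 900 pairs at p = 0.90 gives:

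| rho | Type I error, eyes taken as independent | √(1 + rho) |
|---|---|---|
| 0 | 5.2% | 1.00 |
| 0.1 | 6.0% | 1.05 |
| 0.3 | 7.7% | 1.14 |
| 0.5 | 9.2% | 1.22 |
| 1.0 | 12.0% | 1.41 |

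**Step 3: the plain point-estimate rule.** Section 3.5 also asks only that the observed rate exceed 90%. At a true 90% this happens 48% to 49% of the time at every rho computed, so clustering hardly changes it.

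**Step 4: a test that allows for pairing.** Use Z = (p̂ − 0.90)/√(0.90 × 0.10/1,800 × D). For complete pairs D = 1 + rhô, with rhô = (share with both eyes correct − p̂²)/(p̂(1 − p̂)).

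| rho | Type I error | Power at 92.5% per eye | Power, eyes taken as independent |
|---|---|---|---|
| 0.3 | 4.9% | 94.7% | 97.0% |
| 0.5 | 4.9% | 91.7% | 96.0% |
| 1.0 | 5.1% | 84.4% | 93.3% |

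Over all rho values computed (0, 0.1, 0.2, 0.3, 0.5, 0.7, 0.9, 1) the type I error of this test lies between 4.8% and 5.1%. A plain cluster-robust Wald test gives 5.8% to 6.4% over the same values.

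**The case against.** The strongest reply is that the documents do fix the unit of the success rate. Section 3.5 gives one explicit formula and Section 6.1 adopts it. That stands. A reader might infer from the person-based wording that the unit of the success rate is open and could be picked once the data are known. The documents do not support that for the success rate itself. Nor do they contain any rule for scoring a whole patient as correct, so no pass or fail result under such a rule can be attributed to the plan.

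Second, 778 people can be read as an enrolment count, since a two-eye study recruits people. This is a fair reading and a safe one for power: 778 people with both eyes analysed are equivalent to 1,556/(1 + rho) independent eyes, which is 778 even at rho = 1. It does not tell the analyst how to handle the pairs.

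Third, the share of participants in the primary endpoint may describe how many people the imaging workflow can diagnose, and the joint diagnosis in Annex-1 combines doctors, not eyes. Both readings are plausible. They leave the unit for sensitivity and specificity unstated.

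Fourth, the open-ended list of tests does not exclude a clustered method. That is correct, and nothing in the documents says that eyes will be treated as independent. The point is that no method for pairing is specified and every test named assumes independence.

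**Conclusion.** The concern holds as a gap in the analysis method. The success rate is per eye, the formal test is described for people or patients, pairing is not addressed, and the unit for sensitivity and specificity is missing. If the Annex-1 test is run on eyes as independent, its one-sided type I error exceeds the stated 5% by an amount that depends on rho: slight at 0.1 (6.0%), material at 0.3 to 0.5 (7.7% to 9.2%), and about 12% at the extreme.

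These figures rest on an assumed rho, on 900 complete pairs and on that one way of running the test. A reader might take them as the trial's chance of a false success. They are not: Section 3.5 also requires sensitivity and specificity above 90%, and its plain requirement of an observed rate above 90% barely responds to clustering. Nor do they carry over directly to sensitivity and specificity, where a volunteer may contribute one relevant eye or two. Power for the success rate at 92.5% per eye is not at risk. The plan should be corrected before analysis, but the design and enrolment can stand.

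**What to change.** Keep the per-eye formula in Section 3.5 and make these changes:

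- **Section 6.1 and Annex-1:** state that the eye is the unit of analysis and the patient is the cluster for every proportion, interval and test, including sensitivity and specificity.
- **Annex-1:** test the success rate against 0.90 with variance 0.90 × 0.10/(number of eyes) × D. D is estimated from the data as the cluster-robust variance of the rate divided by its binomial variance. This form also allows for volunteers with one evaluable eye. They seem possible, because the blur exclusion in Section 3.10 applies only when both eyes are affected, although Section 3.9 is worded more broadly.
- **Section 6.2:** state that 778 and 900 count people, while P0 and P1 are per-eye proportions.
- **Sections 3.4 and 3.5:** name the unit for sensitivity and specificity.
- **Section 6.1 and Annex-1:** align the patient wording for the reference diagnosis and the comparison with the software to the eye.

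The cost is protocol and SAP wording and a few lines of code. No extra enrolment is needed: with 900 complete pairs, power at 92.5% per eye stays at 84.4% or more at every rho computed, above the stated 80%. The price is wider intervals, by √(1 + rho), and some power relative to the test that ignores pairing (for example 91.7% instead of 96.0% at rho 0.5). If rho is near 0 the gain is small, with type I error moving from 5.2% to 4.9%. Unequal numbers of eyes per volunteer were not computed.

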3.10. Exclusion Criteria for Volunteers

Fundus images that have corneal or lens opacification that will prevent imaging, and that are not evaluable due to intravitreal hemorrhage or vitreous will not be included in the study. Patients followed or treated for DR will not be included in the study.

- If the volunteer are not diagnosed with diabetes,
- If the potential participant cannot understand the study or informed consent,
- If the volunteer has a history of retinal vascular disease other than diabetic retinopathy, glaucoma, or any other disease that may affect the appearance of the retina or optic disc.
- If the volunteer have had previous intraocular surgery including than cataract, laser intervention on the retina, or previous intraocular intervention for the treatment of diabetic retinopathy,
- If there is a permanent visual impairment in one or both eyes,
- If under the age of 18,

- If the participant is contraindicated for imaging with the fundus imaging systems used in the study,
- Exclude if there is an ambient blur in both eyes severe enough to impede good retinal photography.

If at least one of the above conditions is present, the participant is not included in the study.

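### Section 3.5 passes the accuracy condition on an observed per-eye rate above 90%, and the plan never explicitly makes rejection of Annex-1's H0: P = 0.90 the condition for that pass

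*Combined protocol and SAP*

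**What the plan says.** Section 3.5 defines the measure as "Total correct number / Total number of eyes = Success rate" and sets the bar: "Our criteria for successful completion of the clinical trial: Success rate > 90" per cent. It mentions no test, p-value or confidence limit. It adds that "the Specificity and Sensitivity values should be calculated separately for mtmDR and vtDR and each should be above 90" per cent. That makes five conditions: accuracy, plus sensitivity and specificity for each of two disease levels. Section 3.4 words the primary endpoint similarly, "separately with a minimum 90% sensitivity and 90% specificity", without pooled accuracy.

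Section 6.1 points back to this rule: "The success criterion of the study is specified in Article 3.5". The same section and the Statistical Analysis Plan part of Annex-1 then say that clinical acceptability of the performance measures, overall accuracy among them, will be judged with tests of proportions. The one-sample test is named first in an open list, and the thresholds are left for experts to set.

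Annex-1 says that reaching the 90% success rate will be examined with H0: P = 0.90 against H1: P > 0.90. It and section 6.2 tabulate sample sizes for 5% error and 80% power (reject if Z ≥ 1.6449). The row with 778 people is introduced as an example, and Annex-1 says the minimum effect size still has to be chosen. On enrolment, 3.4 says "The study will include approximately 900 people with diabetes". Annex-1 describes the reference diagnosis as one joint decision per patient.

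**The concern.** An observed rate above 90% and a significant test against 90% are different hurdles. If the observed rate is a little over 90% and H0 is not rejected, 3.5 taken literally says the accuracy condition is met, while the Annex-1 test says performance above 90% has not been shown. The plan does not say which result governs. If that is settled only after the data are seen, the choice can follow the result. A reader could also credit a pass under 3.5 with a 5% error rate that the rule as written does not have.

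The unit adds to the gap. Section 3.5 counts eyes, Annex-1 speaks of patients and people, and nothing says how the two eyes of one patient enter the test.

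**Working it through.** **Inputs.** From the documents: P0 = 0.90, one-sided 5%, critical Z = 1.6449, example row N = 778 with P1 = 0.925 (6.2, Annex-1); about 900 patients (3.4); eyes as denominator (3.5). Assumed, because not given: two gradable eyes per patient (1,800 eyes) and within-patient correlation ρ of correct decisions from 0 to 1.

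**Step 1. The plan's own figure.** The smallest count that rejects H0 at N = 778 is the integer at or above 778 × 0.90 + 1.6449 × √(778 × 0.09) = 700.2 + 13.76 = 713.96, so 714 (91.77%). Exact binomial tails give alpha 0.0530 and power 0.8004 at P = 0.925, as tabulated. The other eight rows reproduce in the same way. The table is therefore correct for the test.

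**Step 2. The 3.5 rule.** More than 90% of 1,800 eyes means at least 1,621 correct.

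**Step 3. The test on eyes, with the patient as cluster.** With two eyes per patient the variance of the count under H0 is 1,800 × 0.09 × (1 + ρ), so the cut-off is 1,620 + 1.6449 × √(162 × (1 + ρ)), rounded up:
- ρ = 0: 1,620 + 1.6449 × 12.73 = 1,640.9, so 1,641.
- ρ = 1: 1,620 + 1.6449 × 18 = 1,649.6, so 1,650.

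**Step 4. Exact probabilities.** The number of correct eyes was obtained by convolution over 900 patients, with P(both correct) = p² + ρp(1 − p).

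| ρ | 3.5 passes, true 90% | 3.5 passes, true 89% | Test cut-off | Test passes, true 90% | Passes 3.5 but fails test, true 90% | Same, true 91% | Power of test, true 92.5% |
|---|---|---|---|---|---|---|---|
| 0 | 48.9% | 8.0% | 1,641 (91.17%) | 5.2% | 43.7% | 50.1% | 98.4% |
| 0.3 | 49.2% | 11.0% | 1,644 (91.33%) | 5.0% | 44.1% | 54.5% | 95.2% |
| 0.5 | 49.3% | 12.7% | 1,646 (91.44%) | 4.8% | 44.5% | 56.8% | 92.1% |
| 0.7 | 49.4% | 14.2% | 1,648 (91.56%) | 4.6% | 44.8% | 58.7% | 88.4% |
| 1 | 48.4% | 15.6% | 1,650 (91.67%) | 5.1% | 43.3% | 57.5% | 84.4% |

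The row ρ = 1 is equivalent to one decision per patient: 811/900 passes 3.5, and the test needs 825/900.

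**Step 5. Sensitivity to the assumptions.** Section 3.10 says "Exclude if there is an ambient blur in both eyes severe enough to impede good retinal photography", which might admit patients with one gradable eye, although the inclusion criterion on blur in 3.9 may keep them out. If 10% or 20% of patients had one gradable eye (illustrative), 3.5 would pass 48.8–49.5% at a true 90% and the test cut-offs would be 91.23–91.73%. With 778 patients and two eyes each, the figures are 49.2–50.4% and 91.26–91.77%. The picture does not change.

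**The case against.** The strongest reply is that the documents already connect the two. Section 6.1 and Annex-1 say acceptability will be judged with tests of proportions, and overall accuracy is among the measures listed. Annex-1 uses the success-rate term of 3.5 when it introduces H0 and H1, and equates clinical success with performing above 90%. On this reading 3.5 states the target and Annex-1 the way to prove it. That is plausible and may well be what was intended. A reader might infer that no test is planned, or that the test has no role in judging success; the documents do not support either. What stands is narrower: the link is not explicit, 6.1 sends the reader to 3.5 for the criterion, and the test sits in an open list with thresholds still to be set.

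It is also fair that the 778 row is only an example and that 6.1 ties the sample size to the incidence of retinopathy. The 80% should not be read as the adopted design power. The gap between the two rules does not depend on that row.

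Any observed-rate rule passes about half the time when the truth lies exactly on the threshold. That is so, and the fall to 8–16% at a true 89% belongs beside it. It does not remove the difference from 5% at the null value that Annex-1 itself chose.

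Finally, a reader might infer a trial-wide type I error near 50%. The documents do not support this: four further conditions must also be met, and neither prevalence nor the dependence between conditions is given, so the joint probability cannot be computed.

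**Conclusion.** The concern holds as a missing explicit link, with an unsettled unit, for the accuracy condition only. The sample-size table is correct for the test it describes, but its 5% and 80% are not properties of the rule written in 3.5. With 900 patients, two gradable eyes each and ρ anywhere from 0 to 1, the literal rule passes 48–49% of trials at a true 90%, against 4.6–5.2% under the clustered test. The two rules disagree in 43–45% of trials at a true 90% and 50–59% at a true 91%. The disputed band runs from just above 90% to about 91.2–91.7% observed.

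A naive per-eye Z-test that ignored pairing would have alpha of about 0.077 at ρ = 0.3 and 0.12 at ρ = 1. No passage prescribes such an analysis, so this is a reason to state the unit and not a fault in a stated method. The point should be fixed before analysis.

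**What to change.** Add to 3.5 and Annex-1 wording such as: *The accuracy condition is met only if H0: P = 0.90 is rejected at one-sided 5%, where P is the per-eye success rate of section 3.5 and the patient is the cluster.*

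Any valid patient-clustered method will do. One example is Z = (p − 0.90) / √(0.90 × 0.10 × D / M), rejecting at Z ≥ 1.6449. Here M is the number of eyes graded, p the share correct, and D = Σ(xᵢ − mᵢp)² / (M p (1 − p)), with mᵢ eyes graded and xᵢ correct in patient i. This is equivalent to requiring a one-sided 95% Wilson lower bound, with M/D as sample size, of at least 90%. In simulation with D estimated from the data its alpha was about 0.045–0.053; a Wald version gave 0.057–0.068 and is less suitable.

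State in 6.1 and Annex-1 that the accuracy threshold is the 90% of 3.5. This should not be carried over to measures such as "Positive Predictive Value of EyeCheckup test for mtmDR and vtDR", for which 3.4 sets no threshold.

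If the sponsor intends an observed-rate rule, 3.5 should say so, and 6.2 and Annex-1 should say that the 5% and 80% describe the test and not the success decision.

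The pass rule for sensitivity and specificity stays as written, with patient-clustered confidence intervals reported.

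**Cost.** No extra patients and a few sentences. It is a real decision if 3.5 was meant literally: the observed accuracy needed rises from just over 90% to about 91.2–91.7%. Power at a true 92.5% with 900 patients is 98% (ρ = 0) to 84% (ρ = 1). If 20% of patients had one gradable eye it would be 97% to 81%.
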